10 DATA MANAGEMENT AND RECORD KEEPING

10.1 Data Management

10.1.1 Data Handling

Data will be recorded at the site on eCRFs and reviewed by the Clinical Research Associate (CRA) during monitoring visits. The CRAs will verify data recorded in the EDC system with source documents. All corrections or changes made to any study data must be appropriately tracked in an audit trail in the EDC system. An eCRF will be considered complete when all missing, incorrect, and/or inconsistent data has been accounted for.

10.1.2 Computer Systems

Data will be processed using a validated computer system conforming to regulatory requirements.

10.1.3 Data Entry

Data must be recorded using the EDC system as the study is in progress. All site personnel must log into the system using their secure user name and password in order to enter, review, or correct study data. These procedures must comply with Title 21 of the Code of Federal Regulations (21 CFR Part 11) and other appropriate international regulations. All passwords will be strictly confidential.

10.1.4 Medical Information Coding

For medical information, the following dictionaries will be used:

- Medical Dictionary for Regulatory Activities (latest) for medical history and adverse events, and
- World Health Organization Drug Dictionary for prior and concomitant medications.

10.1.5 Data Validation

Validation checks programmed within the EDC system, as well as supplemental validation performed via review of the downloaded data, will be applied to the data in order to ensure accurate, consistent, and reliable data. Data identified as erroneous, or data that are missing, will be referred to the investigative site for resolution through data queries.

The eCRFs must be reviewed and electronically signed by the Investigator.

10.2 Record Keeping

Records of patients, source documents, monitoring visit logs, eCRFs, inventory of study product, regulatory documents, and other Sponsor correspondence pertaining to the study must be kept in the appropriate study files at the site. Source data is defined as all information in original records and certified copies of original records of clinical findings, observations, or other activities in a clinical study necessary for the evaluation and reconstruction of the clinical study. Source data are contained in source documents (original records or certified copies). These records will be retained in a secure file for the period as set forth in the Clinical Study Agreement. Prior to transfer or destruction of these records, the Sponsor must be notified in writing and be given the opportunity to further store such records.

11 INVESTIGATOR REQUIREMENTS AND QUALITY CONTROL

11.1 Ethical Conduct of the Study

Good Clinical Practice (GCP) is an international ethical and scientific quality standard for designing, conducting, recording, and reporting studies that involve human patients. Compliance with this standard provides public assurance that the rights, safety, and well-being of study patients are protected, consistent with the principles that have their origin in the Declaration of Helsinki, and that the clinical study data are credible.

11.2 Institutional Review Board/Independent Ethics Committee

The IRB or IEC will review all appropriate study documentation in order to safeguard the rights, safety, and well-being of patients. The study will only be conducted at sites where IRB/IEC approval has been obtained. The protocol, Investigator's Brochure, Informed Consent Form (ICF), advertisements (if applicable), written information given to the patients, safety updates, annual progress reports, and any revisions to these documents will be provided to the IRB/IEC by the Investigator.

Federal regulations and ICH Guidelines require that approval be obtained from an IRB/IEC prior to participation of patients in research studies. Prior to study onset, the protocol, any protocol amendments, ICFs, advertisements to be used for patient recruitment, and any other written information regarding this study to be provided to a patient or patient's legal guardian must be approved by the IRB/IEC.

No drug will be released to the site for dosing until written IRB/IEC authorization has been received by the Sponsor.

11.3 Informed Consent

The ICF and any changes to the ICF made during the course of the study must be agreed to by the Sponsor or designee and the IRB/IEC prior to its use and must be in compliance with all ICH GCP, local regulatory requirements, and legal requirements.

The Investigator must ensure that each study patient is fully informed about the nature and objectives of the study and possible risks associated with participation and must ensure that the patient has been informed of his/her rights to privacy. The Investigator will obtain written informed consent from each patient before any study-specific activity is performed and should document in the source documentation that consent was obtained prior to enrollment in the study. The original signed copy of the ICF must be maintained by the Investigator and is subject to inspection by a representative of the Sponsor, their representatives, auditors, the IRB/IEC and/or regulatory agencies. A copy of the signed ICF will be given to the patient.

11.4 Study Monitoring Requirements

It is the responsibility of the Investigator to ensure that the study is conducted in accordance with the protocol, Declaration of Helsinki, ICH GCP, and applicable regulatory requirements, and that valid data are entered into the eCRFs.

To achieve this objective, the monitor's duties are to aid the Investigator and, at the same time, the Sponsor in the maintenance of complete, legible, well organized and easily retrievable data. Before the enrollment of any patient in this study, the Sponsor or their designee will review with the

Investigator and site personnel the following documents: protocol, Investigator's Brochure, eCRFs and procedures for their completion, informed consent process, and the procedure for reporting SAEs.

The Investigator will permit the Sponsor or their designee to monitor the study as frequently as deemed necessary to determine that data recording and protocol adherence are satisfactory. During the monitoring visits, information recorded on the eCRFs will be verified against source documents and requests for clarification or correction may be made. After the eCRF data is entered by the site, the CRA will review the data for safety information, completeness, accuracy, and logical consistency. Computer programs that identify data inconsistencies may be used to help monitor the clinical study. If necessary, requests for clarification or correction will be sent to Investigators. The Investigator and his/her staff will be expected to cooperate with the monitor and provide any missing information, whenever possible.

All monitoring activities will be reported and archived. In addition, monitoring visits will be documented at the investigational site by signature and date on the study-specific monitoring log.

11.5 Disclosure of Data

Data generated by this study must be available for inspection by the FDA, the Sponsor or their designee, applicable foreign health authorities, and the IRB/IEC as appropriate. Patients or their legal representatives may request their medical information be given to their personal physician or other appropriate medical personnel responsible for their welfare.

Patient medical information obtained during the study is confidential and disclosure to third parties other than those noted above is prohibited.

11.6 Retention of Records

To enable evaluations and/or audits from regulatory authorities or the Sponsor, the Investigator will keep records, including the identity of all participating patients (sufficient information to link records, eg, eCRFs and hospital records), all original signed ICFs, copies of all eCRFs, SAE forms, source documents, and detailed records of treatment disposition. The records should be retained by the Investigator according to specifications in the ICH guidelines, local regulations, or as specified in the Clinical Study Agreement, whichever is longer. The Investigator must obtain written permission from the Sponsor before disposing of any records, even if retention requirements have been met.

If the Investigator relocates, retires, or for any reason withdraws from the study, the Sponsor should be prospectively notified. The study records must be transferred to an acceptable designee, such as another Investigator, another institution, or to the Sponsor.

11.7 Publication Policy

Following completion of the study, the data may be considered for publication in a scientific journal or for reporting at a scientific meeting. Each Investigator is obligated to keep data pertaining to the study confidential. The Investigator must consult with the Sponsor before any study data are submitted for publication. The Sponsor reserves the right to deny publication rights until mutual agreement on the content, format, interpretation of data in the manuscript, and journal selected for publication are achieved.

11.8 Financial Disclosure

Investigators are required to provide financial disclosure information to the Sponsor to permit the Sponsor to fulfill its obligations under 21 CFR Part 54. In addition, Investigators must commit to promptly updating this information if any relevant changes occur during the study and for a period of 1 year after the completion of the study.

12 STUDY ADMINISTRATIVE INFORMATION

12.1 Protocol Amendments

Any amendments to the study protocol will be communicated to the Investigators by Worldwide or the Sponsor. All protocol amendments will undergo the same review and approval process as the original protocol. A protocol amendment may be implemented after it has been approved by the IRB/IEC, unless immediate implementation of the change is necessary for patient safety. In this case, the situation must be documented and reported to the IRB/IEC within 5 working days.

APPENDIX A: SCHEDULE OF PROCEDURES

Study Period	Screening ¹ (≤ 4 weeks)	Placebo	-Label Run-In veeks)		Double-Blind Treatment							EOS	ET ²		
Study Day	≤ -42 days	≤ -18	≤ -4	-1	1	7	14	28	40	42	56	82	84	112	
Visit Visit	1	2	3	ABPM ^{3,4}	45	5	6	7	ABPM ⁴	8	9	ABPM ⁴	10	112	+
Visit Window	1			ADIM		±2 day			ADIM		days	ADIM	10	±5 days	\vdash
Assessment					-	LZ uay	 			 	l			±3 days	1
Signed informed consent	X														+
Eligibility assessment	X		X		X										+
Randomization	A		Λ		X										+
Demographics	X				Λ										-
Medical history	X					1	1		1					1	
Physical examination	X				X ⁶		ł	ł					X	X	X
Height (cm)	X				A								Λ	Λ	Λ
	X	X	X		v	v	X	X		X	X		v	X	X
Weight (kg)		Α	Λ		X	X	Α	Α		Α	A		X	Λ	A
Body mass index	X	₹7			3 7	1	1	W 7			37		X		37
Contact IRT	X	X			X	3 7	 	X			X			V	X
Triplicate standard 12-lead ECG ⁷	X	**	***		X	X	***	***		***	***		77	X	X
Vital signs (PR, RR, OT) ⁸	X X ¹⁰	X	X x 10		X X ¹¹	X	X X ¹¹	X X ¹¹		X	X		X	X	X
Blood pressure ^{8,9}	XIII	X	X ¹⁰		XII	X ¹¹	XII	XII		X ¹¹	X ¹¹		X	X	X
24-hour ABPM device placement				-					***			***			
and start ^{4,12}				X		ļ			X			X			12
24-hour ABPM download at site ⁴					X	 	 			X			X		X ¹³
HIV, HbsAg, and HCV	X														
Urine drug screen	X		X												
Clinical laboratory samples			15											l	
(central laboratory) ¹⁴	X		X ¹⁵		X	X	X	X		X	X		X	X	X
Serum potassium (local and															
central laboratories) ¹⁶	X		X		X	X	X	X		X	X		X	X	X
Serum creatinine (central														l	
laboratory)	X		X		X	X	X	X		X	X		X	X	X
Pregnancy test on WOCBP only ¹⁷	X				X									X	X
FSH ¹⁸	X														
Serum samples for aldosterone					X								X		X
Plasma samples for renin					X								X		X
Serum and plasma samples for															
additional biomarkers ¹⁹					X								X		X
Plasma samples for PK					X^{20}		X^{21}	X^{21}						X	X
Urine samples for UACR	X				X	X	X	X		X	X		X	X	X

Study Period	Screening ¹ (≤ 4 weeks)	Placeb	n-label o Run-In					Do	ukla Dlind	Tucatm	ont.			EOS	ET ²
		(2 weeks)			Double-Blind Treatment							E1-			
Study Day	≤ -42 days	≤-18	≤ -4	-1	1	7	14	28	40	42	56	82	84	112	
Visit	1	2	3	ABPM ^{3,4}	45	5	6	7	ABPM ⁴	8	9	ABPM ⁴	10	11	
Visit Window					±2 days			±3 days						±5 days	
Provide 24-hour urine collection instruction and supplies			X					X			X				
24-hour urine samples for UACR					X					X			X		
Adverse event and concomitant medications	X	X	X		X	X	X	X		X	X		X	X	X
Study drug instruction and dispensing		X ²²			X	X	X	X		X	X				
Administer first/daily dose and record time					X ²³	X ²⁴	X ²⁴	X ²⁴		X ²⁴	X ²⁴				
Study drug accountability and collection of unused study drug			X ²⁵			X	X	X		X	X		X		X

- 1. If a patient is found to be not eligible during Screening, a single rescreening is allowed if the Investigator believes that the patient's condition has changed, and the patient may be eligible before the rescreening tests.
- 2. The Early Termination Visit should be scheduled only for patients who discontinue the study prematurely; assessments should be performed as early as feasible after discontinuation of study drug.
- 3. This visit is to be scheduled within 3 days after the end of the run-in period (Visit 3) for patients undergoing 24-hour ABPM.
- 4. This visit/procedure is for patients undergoing 24-hour ABPM only (a subset of up to 40 patients per treatment group who agree to participate in 24-hour ABPM and still meet eligibility criteria at the end of the run-in period [Visit 3]).
- 5. This visit is to be scheduled within 4 ± 2 days after the end of the run-in period (Visit 3).
- 6. A physical examination will be performed pre-dose.
- 7. Patients should be resting in a supine position for at least 10 minutes prior to assessment.
- 8. Blood pressure and PR will be measured at the same time.
- 9. Triplicate blood pressure measurements should be taken approximately 2 minutes apart with a validated, oscillometric upper arm blood pressure monitor with the patient in the seated position and having rested for at least 10 minutes prior to assessment. Trough-cuff SBP and DBP values will be assessed based on the pre-defined blood pressure measurement guideline throughout the study.
- 10. At Screening and the end of the placebo run-in period (Visit 3), patients must have uncontrolled hypertension, defined as resting trough-cuff seated SBP ≥ 140 mmHg and ≤ 179 mmHg based on the mean of at least 2 current consecutive blood pressure readings in the clinic.
- 11. Blood pressure must be measured prior to study drug administration.
- 12. Blood pressure and heart rate measurements will be obtained every 20 minutes during the interval of 06:00:00 hours to 21:59:59 hours (to coincide with the daytime, awake period), and every 30 minutes during the interval of 22:00:00 hours to 05:59:59 hours (to coincide with the nighttime, sleeping period). During the 24-hour ABPM recording period, a diary will be provided to the patient. Instructions and training will be provided to the site staff, who will in turn provide instructions to the patient.
- 13. If a patient has completed the 24-hour ABPM recording since their last visit, 24-hour ABPM data will be downloaded at the site during the ET Visit.
- 14. Clinical laboratories include chemistry, hematology, coagulation, and urinalysis. See Appendix B for the complete list of clinical laboratory analytes assessed for this study.
- 15. Only clinical chemistry will be conducted at the end of run-in period (Visit 3).
- 16. All patients must have a serum potassium ≤ 4.8 mmol/L at both Screening and the end of the placebo run-in period (Visit 3).
- 17. Serum pregnancy tests will be obtained at Screening, EOS, and ET. A urine pregnancy test will be obtained at pre-dose on Day 1.

- 18. Post-menopausal women only.
- 19. Serum/plasma samples taken during the study will be stored at a central laboratory for determination of various additional biomarkers, including but not limited to galectin-3, N-terminal of the prohormone brain natriuretic peptide, interleukin-6, collagen biomarkers, and C-reactive protein. The panel of biomarkers and time points for analysis will be determined prior to the database lock.
- 20. Plasma samples are to be collected prior to patient's discharge from the unit.
- 21. Plasma samples are to be collected pre-dose. If patients are not dosed in the unit on those days, a PK sample will be collected, and the date and time of the last dose will be recorded.
- 22. Open-label placebo will be dispensed at Visit 2.
- 23. The first dose of the study drug is to be administered.
- 24. The daily dose of the study drug is to be administered.
- 25. If a patient's compliance to medications (including both open-label placebo and current antihypertensive medications) is < 80% or > 120% at Visit 3, he/she will not be eligible for the study and no further visits will be performed.

Abbreviations: ABPM = ambulatory blood pressure monitoring; DBP = diastolic blood pressure; ECG = electrocardiogram; EOS = end of study; ET = early termination; FSH = follicle-stimulating hormone; HbsAg = hepatitis B surface antigen; HCV = hepatitis C virus; HIV = human immunodeficiency virus; IRT = Interactive Response Technology; OT = oral temperature; PK = pharmacokinetic; PR = pulse rate; RR = respiratory rate; SBP = systolic blood pressure; UACR = urine albumin-to-creatinine ratio; WOCBP = women of childbearing potential.

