6.4.2 Day 1 (Visit 4) \pm 2 Days

This visit is to be scheduled within 4 ± 2 days after the end of the run-in period (Visit 3).

The following procedures will be performed at Visit 4:

- Assess eligibility: Patients must have uncontrolled hypertension, defined as resting trough-cuff seated SBP ≥ 140 and ≤ 179 mmHg, based on the mean of at least 2 current consecutive blood pressure readings in the clinic. Prior to randomization, all patients are to have a serum potassium ≤ 4.8 mmol/L at both Screening and the end of the placebo run-in period; and a mean (Visit 1 and Visit 3) eGFR ≥ 15 and ≤ 44 mL/min/1.73 m².
- Record weight;
- Perform physical examination (pre-dose);
- Perform 12-lead ECG in triplicate (patients should be resting in a supine position for at least 10 minutes prior to assessment);
- Obtain vital signs, including pulse rate, respiratory rate, and oral temperature;
- Obtain blood pressure prior to study drug administration;
 - O Blood pressures are to be obtained according to the AHA recommendations for accurate blood pressure measurement. Patients should avoid smoking, caffeine, or exercise within 30 minutes before measurement; empty his or her bladder; then sit quietly in a comfortable chair with back support for at least 10 minutes before measurement and remain still during the measurement. The patient's limb should be supported to measure blood pressure to ensure that the blood pressure cuff is at heart level, using the correct cuff size. Do not take the measurement over clothes. Blood pressure measurements should be performed in the same arm throughout the study. Triplicate blood pressure measurements should be taken approximately 2 minutes apart with a validated, oscillometric upper arm blood pressure

monitor. Trough cuff SBP and DBP values will be assessed based on the pre-defined blood pressure measurement guideline throughout the study. Pulse will be obtained simultaneously with blood pressure measurements;

- Obtain blood sample for clinical laboratory tests (central laboratory; see Appendix B);
- Obtain urine sample for:
 - o Urinalysis (central laboratory; see Appendix B);
 - o Urine pregnancy test for WOCBP only (pre-dose);
 - o UACR; and
 - o 24-hour urine for UACR;
- Obtain serum sample for potassium (local and central laboratories);
- Obtain serum sample for creatinine (central laboratory);
- Obtain plasma sample for PK from all patients (prior to patient's release from the unit);
- Obtain serum sample for aldosterone;

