7.2 Secondary Efficacy Assessments

Twenty-four-hour ABPM monitoring will be assessed at the visits indicated on the Schedule of Procedures (Appendix A) in a subset of up to 40 patients per treatment group. At the end of the run-in period (Visit 3), ABPM will only be assessed for those patients who agree to participate in 24-hour ABPM and still meet all of the eligibility criteria. Blood pressure and HR measurements will be obtained every 20 minutes during the interval of 06:00:00 hours to 21:59:59 hours (to coincide with the daytime, awake period) and every 30 minutes during the interval of 22:00:00 hours to 05:59:59 hours (to coincide with the nighttime, sleeping period).

During the 24-hour ABPM recording period, a diary will be provided to the patient. Instructions and training will be provided to the site staff, who will in turn provide instructions to the patient.

The key secondary efficacy variables include the following:

• Change in trough-cuff seated DBP from baseline to Day 84;

Note: Blood pressure must be measured in triplicate prior to study drug administration at the visits indicated on the Schedule of Procedures (Appendix A). Trough-cuff DBP values will be assessed based on the pre-defined blood pressure measure guideline throughout the study.

- Change in 24-hour mean, daytime mean, nighttime mean, morning mean, last 6 hours of the dosing interval mean, SBP, DBP, MAP, and HR from baseline to Day 84 as measured by 24-hour ABPM in a subset of up to 40 patients per treatment group; and
- Change and percent change in UACR from baseline to Day 84 (for patients with albuminuria [defined as UACR >300 mg/g] or microalbuminuria [defined as UACR in the range of 30 mg/g to 300 mg/g]).

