9.2 Statistical Methods

9.2.1 Demographic and Baseline Comparability

Patient disposition and analysis population data will be tabulated by treatment group with number and percentage of patients. Summary statistics will be provided by treatment group for demographics (eg, age, sex, race, and ethnicity) and for baseline efficacy variables (such as SBP, serum potassium, eGFR, creatinine, DBP, and UACR). For efficacy variables, baseline will be defined as the Day 1 (Visit 4) measurement. If the measurement at this visit is missing, then the last measurement prior to the first dose of randomized study drug will be used.

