9.2.2.2 Secondary efficacy analyses

For continuous secondary efficacy variables, the same ANCOVA model will be used as the primary efficacy analysis. For categorical data, logistic regression or chi-square test will be used. Treatment effects will be evaluated between KBP-5074 doses and placebo.

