APPENDIX B: CLINICAL LABORATORY ANALYTES

Standard Safety Chemistry Panel

Alanine aminotransferase
Albumin
Alkaline phosphatase
Aspartate aminotransferase
Blood urea nitrogen
Chloride
Albumin
Amylase
Bicarbonate
Calcium
Creatine kinase

Chloride Creatine Kinase

Creatinine Estimated glomerular filtration rate¹

Gamma-glutamyl transferase Glucose

Inorganic phosphorus Lactate dehydrogenase

Lipase Potassium
Sodium Total bilirubin
Total protein Uric acid

Calculated by the central laboratory using the Modification of Diet in Renal Disease equation version 4.

Endocrinology

Follicle-stimulating hormone (FSH) for post-menopausal women only¹

Post-menopausal is defined as amenorrheic for at least 1 year AND have a serum FSH level of > 20 mIU/mL.

Hematology

Hematocrit Hemoglobin

Platelets Red blood cell count

White blood cell count and differential

Urinalysis

Bilirubin Blood
Glucose Ketones
Leukocyte esterase Microscopy¹

Nitrite pH

Protein Specific gravity

Urobilinogen

Additional Urinalysis

Urine drug screen

Percent change in urine albumin-to-creatinine ratio (UACR) for spot urine specimen UACR for 24-hour urine specimen

Microscopy is performed only as needed based on positive dipstick test results.

Coagulation

Activated partial thromboplastin time

International normalized ratio

Prothrombin time

Serology

Hepatitis B surface antigen

Human immunodeficiency virus

Hepatitis C virus

Biomarkers

Aldosterone Renin

Serum/plasma samples taken during the study will be stored at a central laboratory for determination of various additional biomarkers, including but not limited to galectin-3, N-terminal of the prohormone brain natriuretic peptide, interleukin-6, collagen biomarkers, and C-reactive protein. The panel of biomarkers and time points for analysis will be determined prior to the database lock.

Pregnancy Test

Serum/urine pregnancy tests will be administered to all women patients of childbearing potential.

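### Spot UACR is taken at Screening and Day 1 in every patient, but only Day 1 serves as baseline, so a second valid pre-randomisation reading adds no precision to a key secondary analysis

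*Combined protocol and SAP*

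**What the plan says.** Section 6.2 (Screening) and Section 6.4.2 (Day 1) each list a urine sample for UACR. The Appendix A row "Urine samples for UACR" marks both visits, then Days 7, 14, 28, 42, 56, 84 and 112 and early termination, with no footnote limiting it to a subset. In Section 6.4.2 the first randomised dose follows the Day 1 samples, so both readings precede treatment.

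Section 9.2.1 names UACR among the baseline efficacy variables and says: "For efficacy variables, baseline will be defined as the Day 1 (Visit 4) measurement". The fallback is: "If the measurement at this visit is missing, then the last measurement prior to the first dose of randomized study drug will be used".

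Section 7.2 lists "Change and percent change in UACR from baseline to Day 84" among the key secondary efficacy variables. On the model, Section 9.2.2.2 says: "For continuous secondary efficacy variables, the same ANCOVA model will be used as the primary efficacy analysis". The covariate named in that primary model (Section 9.2.2.1) is baseline SBP.

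On specimens, Day 1 also has "24-hour urine for UACR", repeated at Days 42 and 84 but not taken at Screening. Appendix B lists "Percent change in urine albumin-to-creatinine ratio (UACR) for spot urine specimen", which ties percent change to the spot sample.

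**The concern.** A single spot value carries visit-to-visit noise, and that noise limits how much of the Day 84 variation a baseline covariate can remove. A second reading taken before treatment can remove more. Because it precedes randomised treatment, it cannot bias the comparison between arms. UACR is not an eligibility criterion, so the Screening reading is not truncated by selection, and background antihypertensive doses are in general meant to stay fixed from screening onward (Section 3.1).

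The trial is sized on SBP only, and UACR is analysed in the subset with albuminuria or microalbuminuria. Precision from samples already scheduled is therefore worth having. At stake is the width of the confidence interval for a key secondary variable. The validity of the comparison is not in question.

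**Working it through.** **The plan's own figures.** There is none for UACR. The SBP sample size in Section 9.2.7 reproduces: 2 × (1.96 × 15/5)² = 69.1, so 70 evaluable per group, and 70/0.875 = 80 at 12.5% dropout. This point does not affect it.

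**Assumed inputs (log scale, none from the documents).** Between-patient SD *b* 1.0–1.4; within-patient visit SD *w* 0.30–0.60; SD of true individual change from Day 1 to Day 84 *c* 0.3–0.5; SD of drift between Screening and Day 1 *d* 0–0.2, then widened to 0.35 and 0.5.

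**Model.** Day 1 = level + noise; Screening = level + drift + noise; Day 84 = level + change + noise. Write A = b² + w² (variance of Day 1), S = b² + w² + d² (variance of Screening) and T = b² + c² + w² (variance of Day 84). Every covariance is b². Residual variance of Day 84:

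- Day 1 only: V1 = T − b⁴/A
- both as separate covariates: V2 = T − b⁴(A + S − 2b²)/(AS − b⁴)
- simple mean of the two: Vm = T − 4b⁴/(A + S + 2b²)

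**Largest gain with drift 0–0.2** (b 1.4, w 0.6, c 0.3, d 0): T = 2.41, A = S = 2.32. V1 = 2.41 − 3.8416/2.32 = 0.754. V2 = 2.41 − 3.8416 × 0.72/1.5408 = 0.615. Ratio 0.815.

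**Smallest gain with drift 0–0.2** (b 1.0, w 0.3, c 0.5, d 0.2): T = 1.34, A = 1.09, S = 1.13. V1 = 1.34 − 1/1.09 = 0.423. V2 = 1.34 − 0.22/0.2317 = 0.391. Ratio 0.924.

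The variance cut is thus 8% to 18%. Interval width scales with √0.924 = 0.961 to √0.815 = 0.903, so it is 4% to 10% narrower. In patient numbers, 1/0.924 − 1 = 8% and 1/0.815 − 1 = 23% more patients in the UACR set.

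**Larger drift.** Appendix A allows Screening up to 42 days before Day 1. If true change accumulates as a random walk, the assumed 84-day SD of 0.3–0.5 scales by √(42/84) to 0.21–0.35. Least favourable settings for two covariates (b 1.0, w 0.3, c 0.5):

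- d = 0.35: V2 = 1.34 − 0.3025/0.3216 = 0.399; ratio 0.945 (cut about 5%)
- d = 0.5: V2 = 1.34 − 0.43/0.4606 = 0.406; ratio 0.962 (cut about 4%, interval 2% narrower)

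**Simple mean against two covariates.** With b 1.4, w 0.3, c 0.3, d 0.5: T = 2.14, A = 2.05, S = 2.30. V1 = 0.266, Vm = 2.14 − 4 × 3.8416/8.27 = 0.282 (ratio 1.06, a loss) and V2 = 0.249 (ratio 0.93, a gain).

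**Cross-check by correlations.** With equal correlation r between all readings, the ratio for the mean is (1 + 2r)/(1 + r)²: 0.889 at r = 0.5 and 0.776 at r = 0.9. Simulation gave 0.856 at r = 0.6 and 0.794 at r = 0.8, against 0.859 and 0.802 by formula. With correlations 0.8 (Screening–Day 1), 0.8 (Day 1–Day 84) and 0.7 (Screening–Day 84), V1 = 0.36. The mean gives 1 − 1.5²/3.6 = 0.375, ratio 1.042. Two covariates give 1 − 0.234/0.36 = 0.35, ratio 0.972. The direction agrees: two covariates do not raise the residual variance, while the mean can.

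**The case against.** The Day 1 rule is clear, pre-specified, unbiased and the same for all efficacy variables. UACR has no stated power or decision rule, so an interval a few percent narrower changes no decision in the plan. That stands, and it keeps this a minor, optional improvement.

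The gain is measured against a model the plan does not name. Read literally, Sections 9.2.2.1 and 9.2.2.2 adjust UACR for baseline SBP and state no log transformation. That also stands: the percentages apply once a log-UACR ANCOVA on spot urine is specified, which is why the fix states that model. If the 24-hour specimen led instead, Screening would have no like-for-like value. Appendix B favours spot for percent change, but the plan does not settle the endpoint specimen.

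Every UACR variance is assumed, Screening may be about six weeks before Day 1, and diuretic doses may be adjusted. This stands as a limit on size. It is the reason for the wider drift range and for preferring two covariates.

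A reader might infer more than the documents support:

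- **That patients near 30 mg/g are misclassified because only Day 1 places them.** The endpoint is restricted by albuminuria status ("Change and percent change in UACR from baseline to Day 84 (for patients with albuminuria" and the microalbuminuria range), but no section says which visit defines that status, so this cannot be asserted.
- **That the Screening value is never used.** It is the fallback when Day 1 is missing.
- **That the Day 1 baseline biases the result.** Randomisation protects it.

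**Conclusion.** The point holds as an efficiency matter. The plan collects two spot UACR readings before randomised dosing in every patient and uses one, except when Day 1 is missing. The gain from using both is modest: about 8% to 18% of residual variance with drift SD 0–0.2, and about 4% to 5% at worst with drift SD 0.35–0.5. These figures rest on the assumed log SDs, on spot urine, and on a log-UACR ANCOVA with Day 1 only as the comparator. None of those SDs is in the documents. No conclusion is drawn about membership of the UACR ≥ 30 mg/g set. The primary endpoint and sample size are unaffected.

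**What to change.** In Section 9.2.2.2, state before unblinding that Day 84 spot UACR is analysed by ANCOVA on the log scale, with Screening log UACR and Day 1 log UACR entered as two separate covariates rather than averaged. Leave Day 1 as the baseline for change and percent change, and leave the Day 84 endpoint as it is. Add a short rule, applied without regard to treatment arm, for patients missing the Screening value.

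The cost is a sentence or two of text, one extra covariate (about one residual degree of freedom) and that missing-value rule. No sample or visit is added.
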